APPENDIX L: CASE REPORT FORMS112
APPENDIX M: INVESTIGATIONAL PLAN REVISIONS.....113

LIST OF TABLES

Table 1. Follow-up Windows	26
Table 2. Data Collection Summary.....	27
Table 3. Unavoidable Events	38
Table 4. Heart Mate II Study Rates	44
Table 5. Study Oversight Contact Information.....	60
Table 6. Investigator Reporting Responsibility	68
Table 7. Sponsor Reporting Responsibility	70

TABLE OF FIGURES

Figure 1. Study Design Flowchart	17
Figure 2 Annual Survival versus Hospitalization versus NYHA	58

Trial Contact Information

Sponsor, Manufacturer & Distributor	Sunshine Heart, Inc. [name] Tele: [name] [contact] www.sunshineheart.com
-------------------------------------	---

Clinical/Technical Support [contact]-SHCPULSE)

INTRODUCTION

PURPOSE

Sunshine Heart is sponsoring a prospective, multi-center, randomized trial to assess the safety and efficacy of the C-Pulse® System (“C-Pulse”).

The purpose of the study is to determine whether the use of the C-Pulse as a treatment for patients in moderate to severe heart failure (HF) has demonstrated safety and efficacy, such that the C-Pulse System merits Food and Drug Administration (FDA) approval to market the device in the United States.

STUDY SIZE AND DURATION

This clinical study is anticipated to commence October 2012. The enrollment and 12 month follow-up duration of the study is expected to be 3.5 years. The primary study population will include 388 subjects enrolled and randomized in up to 40 centers in the United States (US) and potentially additional sites in Canada. The treatment group will include 194 subjects randomized to and implanted with C-Pulse® System and the control group will include 194 subjects randomized to and followed according to the same follow-up schedule as the treated subjects. All patients must be consented prior to performing any study related procedures. A patient is considered enrolled upon signing the informed consent. To minimize the burden to the patient, data collected as standard of care and not for the specific reason for study eligibility may be used for baseline data points as outlined in the informed consent. These tests will suffice for the baseline dataset if collected within the specified baseline data collection timeframe prior to implant. The subjects will be assigned a screening number upon signing the consent.

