where HR is the hazard ratio; the ratio of the C-Pulse treatment group worsening heart failure event hazard relative to the Control group worsening heart failure event hazard. This is designed to demonstrate that C-Pulse[®] therapy increases the freedom from worsening heart failure events as compared to Control as evidenced by a HR that is less than 1 and the upper bound of the two-sided 95% confidence interval for the HR excludes 1. All occurrences of worsening heart failure events will be included in the primary endpoint analysis. Details of the analysis methods can be found in the Statistical Analysis Plan.

Primary Efficacy Endpoint Sample Size

Sample size was estimated using SAS v9.2 software under two sided test for a difference in freedom from worsening heart failure. For the purposes of sample size estimation, a time to first event analysis was used to provide a conservative estimate of the required number of events and subjects. The minimum required sample size and total number of worsening heart failure events was calculated under the following assumptions:

- Significance level = 0.05
- Power = 0.80
- Proportion for 6 month freedom from worsening heart failure event in Control group = 0.72
- Underlying treatment effect on the hazard ratio scale: HR = 0.70
- Accrual time of 2.5 years
- Minimum follow-up of 12 months
- 10% Attrition per year
- 1:1 allocation ratio

Under the above assumptions a total of 265 subjects with at least one worsening heart failure events are required to be observed to ensure adequate power which indicates a total of 388 subjects randomized. As the primary analysis will include all worsening heart failure events in a multiple event analysis, the power for the detection of a difference in freedom from worsening heart failure event may be greater than 80%.

Justification for Primary Efficacy Endpoint Sample Size Assumptions

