The primary safety endpoint is 12 month freedom from serious adverse events that are adjudicated definitely related to device, therapy or procedure and resulting in either surgical intervention or death. All serious adverse events that are adjudicated by CEC to be definitely related to device, therapy or procedure and result in either surgical intervention or death will be included in the analysis. Events will be reported by number of event and proportion of subjects with event along with the ninety-five percent binomial exact confidence limits. Only first event counts towards the endpoint for each subject.

The proportion of C-Pulse[®] subjects free from serious adverse events that are adjudicated definitely related to device, therapy or procedure and result in surgical intervention or death through 12 months following implant and will be compared to the performance goal (PG) of 0.60.

The hypotheses are:

$$H_0: \Pi \leq PG,$$

$$H_A: \Pi > PG,$$

where Π is the 12 month freedom from serious adverse events that are definitely related to device, therapy or procedure and resulting in either surgical intervention or death and PG is the performance goal. If the lower, two-sided, 95% confidence bound is greater than 0.6 the objective will be met.

Primary Safety Endpoint Sample Size

Sample size was estimated for a combined freedom from serious adverse events adjudicated definitely related to device, therapy or procedure resulting in surgical intervention (to repair, replace or remove the implanted device) or death. The minimum required sample size and total number of device related deaths and device related surgical intervention events was calculated under the following assumptions:

- Significance level = 0.05
- Power = 0.80
- 12 month freedom from serious adverse events definitely related to device, therapy or procedure resulting in either surgical intervention (to repair, replace or remove implanted device) or death event of 70%.
- Minimum follow-up of 12 months

Under the above assumptions a minimum of 182 subjects are required.

Justification for Primary Safety Endpoint Sample Size

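### The safety sample size of 182 allows for no attrition, although the efficacy calculation assumes 10% a year for the same subjects; the 194-subject device arm keeps about 80% power only if safety losses stay at or below about 6%

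*Combined protocol and SAP*

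**What the plan says.** The section Primary Safety Endpoint defines a single-arm proportion of device subjects free at 12 months from definitely related serious events that lead to surgical intervention or death. It "will be compared to the performance goal (PG) of 0.60". Results are reported "along with the ninety-five percent binomial exact confidence limits", and the success rule is: "If the lower, two-sided, 95% confidence bound is greater than 0.6 the objective will be met".

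The section Primary Safety Endpoint Sample Size lists four inputs: "Significance level = 0.05", power 0.80, 70% freedom at 12 months, and at least 12 months of follow-up. It concludes: "Under the above assumptions a minimum of 182 subjects are required". No attrition or non-implantation term is listed, and no formula is named.

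The section Primary Efficacy Endpoint Sample Size does include such a term: "10% Attrition per year". Study Size and Duration fixes the arm: "The treatment group will include 194 subjects randomized to and implanted with" the device. Analysis Population restricts the safety evaluation to implanted subjects and foresees that some randomized subjects may not receive the implant. Handling of Missing Data gives a censoring rule for primary efficacy and additional analyses for walk distance, KCCQ and LVEF. It gives none for primary safety.

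**The concern.** The device arm in the safety calculation is half of the subjects in the efficacy calculation, and the safety endpoint runs over 12 months, during which the efficacy inputs expect 10% to be lost. One calculation allows for that loss and the other does not.

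Incomplete follow-up is foreseeable from the protocol itself. Data Collection Overview has subjects who are transplanted or move to another device exit the study, and follows device subjects only until removal. Subject Withdrawal or Loss to Follow-Up ends observation at either event. A simple binomial proportion cannot handle censoring, so each implanted subject who leaves early without an event must be dropped, counted as event-free, or handled by some other stated rule. The first choice costs power. The second favours the device. What is at stake is the stated chance of meeting a co-primary objective and the credibility of the estimate behind it.

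**Working it through.** **Inputs.** From Primary Safety Endpoint and its sample-size section: goal 0.60, assumed freedom 0.70, lower two-sided 95% limit (2.5% in the tested tail), exact limits, target power 0.80, stated minimum 182. From Study Size and Duration: 194 device subjects. From Primary Efficacy Endpoint Sample Size: 10% attrition per year.

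**Step 1: reproduce 182.** One-sample normal approximation with null and alternative variances:

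n = [1.960 × √(0.60 × 0.40) + 0.8416 × √(0.70 × 0.30)]² / 0.10² = (0.9602 + 0.3857)² / 0.01 = 181.1, rounded up to **182**.

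The match is exact with no loss term. That this formula was used is an inference from the match.

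**Step 2: the margin.** 194 − 182 = 12, and 12/194 = 6.2%.

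**Step 3: denominator at the plan's attrition figure.** 194 × 0.90 = 174.6, so 174 to 175, below 182.

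**Step 4: exact power.** For each n, take the smallest event-free count r whose Clopper-Pearson lower two-sided 95% limit exceeds 0.60; power is P(X ≥ r) for X ~ Binomial(n, 0.70).

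| Evaluable n | Situation | r needed | Exact power |
|---|---|---|---|
| 194 | no loss | 131 | 79.8% |
| 184 | 5% loss | 124 | 80.4% |
| 182 | stated minimum | 123 | 78.7% |
| 181 | just over 6% loss | 122 | 80.1% |
| 175 | 10% loss | 119 | 74.7% |
| 174 | 10% loss | 118 | 76.3% |
| 164 | 15% loss | 112 | 71.6% |

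Exact power is saw-toothed in n, so differences of 1 to 3 points between neighbouring values mean little. The average over n = 171 to 179 is 76.9%, hence about 75-77% at 10% loss. The saw-tooth does not rescue the figure: no n from 150 to 180 reaches 80%. At n = 175, 80% power would need a true freedom of about 70.6%.

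**Step 5: normal approximation against exact.** By normal approximation power is 80.2% at 182 and 82.7% at 194; with exact limits it is 78.7% and 79.8%. The method alone leaves 194 at 80% to the precision the protocol uses.

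**Step 6: early exits counted as event-free.** As an illustration, suppose 10% exit early and on average half of their event risk goes unobserved. The apparent freedom becomes 0.70 + 0.10 × 0.5 × 0.30 = 0.715, and P(X ≥ 131) at n = 194 is about 90%. Power rises only because events are missed: the estimate is 1.5 points too high.

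**The case against.** The best defence has four parts.

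- **182 is called a minimum, it reproduces, and the arm has 194.** This stands. There is no arithmetic error, and the 12-subject margin must be credited: at 5% loss exact power is 80.4%.
- **Exact limits do no harm at 194.** This stands. A reader might infer that the planned arm fails 80% because the sizing used a normal approximation while the analysis uses exact limits. The figures do not support that: 79.8% is a local trough, with 81.1% at 193 and 82.6% at 195, and 80% at 194 needs a true freedom of 70.03% in place of 70%.
- **The 10% is an efficacy input and need not carry over one for one.** This stands in part. Safety includes all implanted subjects, not completers only. A subject with a qualifying event before leaving still counts, and a removal caused by a definitely related serious event is itself an endpoint event. Ten percent is therefore a planning figure for safety losses, not a measured one. It is nevertheless the only attrition figure in the document, it covers the same subjects, and the safety section gives no reason to replace it with zero.
- **The shortfall is small.** It corresponds to about 0.6 points in the assumed freedom rate, and low power against a performance goal does not inflate type I error. Both statements are true. They limit the severity but do not reconcile the two calculations or supply the missing counting rule.

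Two further readings go beyond the documents. Power of 73.7% at n = 166 requires an assumed 5% non-implantation on top of 10% attrition, and no non-implantation rate is given. Nor is it settled that a safety failure would block all secondary testing: Secondary Efficacy Endpoints requires both primary objectives to be met, while Type I Error Control for Secondary Objectives names efficacy only.

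**Conclusion.** The concern holds in a limited form. The safety calculation omits attrition that the efficacy calculation assumes for the same subjects. The 194-subject arm gives about 80% exact power if all losses from the safety denominator, including subjects not implanted, stay at or below about 6%. At 10% loss about 175 remain, under the stated minimum of 182, and power at 70% true freedom is about 75-77%; the risk of missing the goal when the assumption is true rises from 20% to about 23-25%.

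That result rests on two assumptions: that the efficacy attrition figure applies to the safety denominator, and that early exits without an event leave it. The combined document states neither. If such subjects are counted as event-free, the problem becomes bias toward the device rather than lost power. Either way, the stated 80% is not supported as written under the plan's own attrition figure.

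**What to change.** In Primary Safety Endpoint Sample Size, restate the calculation with the exact test and the 10% attrition: about 175 evaluable device subjects, power about 75-77% at 70% true freedom, and about 80% only with losses up to about 6%. Show how many of the 194 are expected to be implanted, and give the event-free count needed for the observed denominator (for example 131 of 194, or 119 of 175).

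In Primary Safety Endpoint or Handling of Missing Data, state how implanted subjects with less than 12 months of follow-up and no event are counted, without treating them as event-free in the primary safety analysis. If a separate analysis plan already contains such a rule, the protocol should cite it.

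Enrollment, performance goal and success criterion are unchanged. The cost is a text change and a slightly less favourable stated power.

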1. If the test statistic for the primary endpoint crosses the futility threshold, the DSMB may recommend that enrollment be discontinued for futility.
2. If the test statistic for the primary endpoint crosses the efficacy threshold the DSMB may make one of the following recommendations:
 - A. recommend that the trial be stopped for efficacy
 - B. recommend that the control arm be dropped as the enrollment of the treatment arm continues in order to achieve a minimum of 12 months of follow-up on a defined number of implanted subjects
 - C. recommend that the trial continues as planned to obtain a better precision on the treatment effect.
3. If neither the futility nor the efficacy boundaries are crossed, the DSMB may recommend that trial enrollment and follow-up continue as planned.

Secondary Efficacy Endpoints

The following secondary endpoints will be analyzed according to the objectives and hypothesis tests given below. Testing of the hypothesis driven secondary efficacy objectives will be conducted only in the event the primary efficacy objective and primary safety objectives are met, thereby preserving an overall Type I error rate of 5%. The secondary efficacy endpoints and associated analyses are described below:

1. Improvement in 6 Minute Hall Walk at 12 months

The improvement in 6 Minute Hall Walk will be computed as the difference between the baseline and follow-up value at 12 months. Subjects not evaluated at 12 months due to prior VAD implant, heart transplant or death will have the worst possible outcome imputed for improvement. Subjects unable to perform the 6MHW will have a value of 0 for the 12 month result. Improvement at 12 months will be compared between treatment groups under the following hypotheses.

Hypotheses

$$H_0: DT = D_c$$

$$H_A: DT \neq D_c,$$

where DT represents the distribution of improvement in 6MHW for the Treatment and D_c the distribution of improvement in 6MHW for Control. Details of the analysis methods can be found in the Statistical Analysis Plan.

2. Improvement in 6 Minute Hall Walk at 18 months

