The improvement in 6 Minute Hall Walk will be computed as the difference between the baseline and follow-up value at 18 months. Subjects not evaluated at 18 months due to prior VAD implant, heart transplant or death will have the worst possible outcome imputed for improvement. Subjects unable to perform the 6MHW will have a value of 0 for the 18 month result. Improvement at 18 months will be compared between treatment groups under the following hypotheses.

Hypotheses

$$H_0: DT = D_c$$

$$H_A: DT \neq D_c,$$

where DT represents the distribution of improvement in 6MHW for the Treatment and D_c the distribution of improvement in 6MHW for Control. Details of the analysis methods can be found in the Statistical Analysis Plan.

3. Improvement in LVEF at 12 months

The improvement in LVEF will be computed as the difference between the baseline and follow-up values at 12 months. Subjects not evaluated at 12 months due to prior VAD implant, heart transplant or death will have the worst possible outcome imputed for improvement. Improvement at 12 months will be compared between treatment groups under the following hypotheses.

Hypotheses

$$H_0: DT = D_c$$

$$H_A: DT \neq D_c,$$

where DT represents the distribution of improvement in LVEF for Treatment and D_c the distribution of improvement in LVEF for Control. Details of the analysis methods can be found in the Statistical Analysis Plan.

4. Days Alive and Out of Hospital due to Worsening Heart Failure through 12 Months

The total days alive and out of hospital due to worsening heart failure following randomization through 12 months will be computed for each subject in a similar fashion to DAOH except hospitalization days for reasons other than heart failure will not be subtracted from the total possible days. The treatment groups will be compared under the following hypotheses.

Hypotheses

$$H_0: DT = D_c$$

$$H_A: DT \neq D_c,$$

where DT represents the distribution of days alive and out of hospital due to worsening heart failure for Treatment and D_c the distribution of days alive and out of hospital due to worsening heart failure for Control. Details of the analysis methods can be found in the Statistical Analysis Plan.

5. Days Alive and Out of Hospital through 12 Months

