The total days alive and out of hospital following randomization through 12 months will be computed for each subject. Each subject will contribute a maximum of 365 days alive and outside of hospital following randomization. Days the subject is in hospital will be subtracted from the maximum. For subjects with a death or study exit prior to 12 months, the days from the date of death or study exit to the date at 365 days post randomization will be subtracted from the total. The treatment groups will be compared under the following hypotheses.

Hypotheses:

$$H_0: DT = D_c$$

$$H_A: DT \neq D_c,$$

where DT represents the distribution of days alive and out of hospital for Treatment and D_c the distribution of days alive and out of hospital for Control. Details of the analysis methods can be found in the Statistical Analysis Plan.

6. Improvement in KCCQ Score at 12 months

The improvement in overall KCCQ score will be computed as the difference between the baseline and follow-up scores at 12 months. Subjects not evaluated at 12 months due to prior VAD implant, heart transplant or death will have the worst possible outcome imputed for improvement. Improvement at 12 months will be compared between treatment groups under the following hypotheses.

Hypotheses

$$H_0: DT = Dc$$

$$H_A: DT \neq Dc,$$

where DT represents the distribution of improvement in Overall KCCQ Score for Treatment and Dc the distribution of improvement in Overall KCCQ for Control. Details of the analysis methods can be found in the Statistical Analysis Plan.

Additional Supportive Analyses

1. Components of primary efficacy endpoint

The components of the primary endpoint will be summarized individually by treatment group. The proportions of subjects with heart failure related hospitalization, LVAD implant, heart transplant, and death due to worsening heart failure will be reported and the time to each event will be described by Kaplan-Meier curves. The number and proportion of subjects with hospitalization due to worsening heart failure as well as the rate per patient year will be summarized.

2. All-cause mortality

All-cause mortality will be summarized by treatment group by number and percent of subjects as well as by Kaplan-Meier curves.

3. Major cardiac events

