The poolability of the primary efficacy endpoint across clinical sites will be assessed using a covariate adjusted proportional hazards regression model including an interaction term for clinical site and treatment group. In the event statistical evidence of a difference in treatment effect by site is found, an analysis utilizing a random effects model with a random effect for site will be conducted.

Type I Error Control for Secondary Objectives

The secondary efficacy objectives will be tested in a hierarchical fashion in the order listed only in the event the primary efficacy objective is met, thereby preserving an overall Type I error rate of 5%.

Handling of Missing Data

For the primary efficacy analysis, subjects lost to follow-up or explanted will be censored at the date of the last assessment.

Additional analyses of the follow-up assessments of KCCQ, six minute walk and LVEF will be conducted to assess the impact of missing data at month 12. The Wilcoxon Sign-Rank test with the worst rank imputed for data missing due to death, LVAD transplant, heart transplant or explant (in order of time to outcome) will be used to assess treatment differences in the continuous parameters while including subjects who withdrew from randomized treatment prior to the 12 month assessment. Multiple imputation analyses will be conducted to assess the robustness of the study results against data missing due to losses to follow-up and study non-compliance or un-interpretable test results.

Impact of Covariates on the Potential Treatment Differences

Additional exploratory statistical analyses of the primary and secondary study results will be conducted to assess for impact of selected baseline and follow-up parameters on the observed treatment differences. This will involve the stratification of results by categorical parameters and covariate adjusted regression analyses for the assessment of interaction with randomization assignment. Of particular interest will be an assessment for any treatment differences in the efficacy or safety parameters by gender. Other baseline covariates of interest will include classification based on race/ethnicity, age at implant, INTERMACS profile, NYHA, etiology (ischemic/non-ischemic), CRT/ICD therapy, angina, arrhythmia, hyperlipidemia and diabetes and the continuous covariates of baseline six-minute walk, KCCQ and MLWHF.

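### The protocol compares raw change in 6-minute walk, LVEF and KCCQ between arms and specifies no baseline adjustment; adding it would gain modest precision for KCCQ and little for the walk

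*Combined protocol and SAP*

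**What the plan says.** Under Secondary Efficacy Endpoints, four of the six items are defined as change scores:

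- Item 1, the 12-month walk: "The improvement in 6 Minute Hall Walk will be computed as the difference between the baseline and follow-up value at 12 months".
- Item 2, the 18-month walk: "The improvement in 6 Minute Hall Walk will be computed as the difference between the baseline and follow-up value at 18 months".
- Item 3, LVEF: "The improvement in LVEF will be computed as the difference between the baseline and follow-up values at 12 months".
- Item 6, KCCQ: "The improvement in overall KCCQ score will be computed as the difference between the baseline and follow-up scores at 12 months".

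The null hypothesis is equality of two distributions, "where DT represents the distribution of improvement in 6MHW for the Treatment and D_c the distribution of improvement in 6MHW for Control", with parallel wording for LVEF and KCCQ. No covariate is named. For the 12-month endpoints, "Subjects not evaluated at 12 months due to prior VAD implant, heart transplant or death will have the worst possible outcome imputed for improvement"; item 2 has the same rule at 18 months. Each item then closes with "Details of the analysis methods can be found in the Statistical Analysis Plan".

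Baseline adjustment appears only under Impact of Covariates on the Potential Treatment Differences. There it is exploratory and aimed at interaction with the randomized assignment. The list includes "the continuous covariates of baseline six-minute walk, KCCQ and MLWHF"; baseline LVEF is not named. The section on Type I error control tests the six secondaries in the order listed.

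**The concern.** When the outcome is change from baseline, subjects who start low tend to rise and subjects who start high tend to fall. An unadjusted comparison leaves that predictable variation in the error term. Conditioning on the baseline value removes it without biasing a randomized comparison. LVEF and walk distance are entry criteria and KCCQ is a scheduled baseline assessment, so no new data are needed.

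What is at stake is precision on endpoints for which the protocol states no power, standard deviation (SD) or effect size. Their sample size is inherited from the primary endpoint.

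**Working it through.** **1. The plan's own figure.** The only sample size is the primary one: 388 randomized and 265 subjects with an event (Primary Efficacy Endpoint Sample Size).
- Control hazard: -ln(0.72)/0.5 = 0.657 per year. Device hazard: 0.70 × 0.657 = 0.460.
- With 2.5 years' accrual and 12 months' minimum follow-up, the event probabilities without attrition are 0.745 and 0.625, average 0.685. Then 388 × 0.685 = 266, against 265 stated.
- Schoenfeld's formula needs 247 events. With 10% yearly loss the average probability is 0.627, and 247/0.627 = 394, within 3% of 388.

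So the stated N reproduces, and the secondaries inherit 194 per arm. They have no stated figure of their own to check.

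**2. Gain with no worst ranks.** Let rho be the baseline/follow-up correlation and k the ratio of baseline SD to follow-up SD. In units of the follow-up variance, change has variance 1 + k² - 2·rho·k, and the baseline-adjusted outcome has 1 - rho². The ratio is (1 - rho²)/(1 + k² - 2·rho·k), which is (1 + rho)/2 when k = 1. The documents give neither rho nor k, so both are assumptions.

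| rho | ratio, k = 1 | ratio, k = 0.6 |
|---|---|---|
| 0.3 | 0.65 | 0.91/1.00 = 0.91 |
| 0.5 | 0.75 | 0.75/0.76 = 0.99 |
| 0.7 | 0.85 | 0.51/0.52 = 0.98 |
| 0.8 | 0.90 | 0.36/0.40 = 0.90 |

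The ratio is 1 when rho = k, so the gain can vanish. The narrow-baseline column matters for the walk: Inclusion Criterion 7 limits baseline to 175-375 m. If baseline were uniform over that range (an assumption), its SD would be 200/√12 = 58 m.

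**3. Effect of the worst ranks.** Simulation with 194 per arm and 3,000 trials per setting compared a Wilcoxon test on change with rank analysis of covariance. The effect was set to give about 80% power for the change test when nobody is at the worst rank. Power, unadjusted to adjusted:

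| Share at worst rank | rho 0.5, k = 1 | rho 0.7, k = 1 | rho 0.5, k = 0.6 | rho 0.7, k = 0.6 |
|---|---|---|---|---|
| 0% | 78.3 to 87.7% | 78.7 to 84.7% | 78.4 to 79.1% | 78.3 to 79.0% |
| 20% | 43.8 to 46.0% | 42.7 to 44.6% | 41.5 to 41.8% | 42.7 to 43.0% |
| 35% | 21.0 to 21.6% | 21.9 to 22.3% | 21.6 to 22.0% | 21.8 to 21.6% |

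Subjects tied at the worst rank carry outcome variation that baseline does not explain in this simulation, so the gain shrinks as their share grows.

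**4. Endpoint-shaped simulations.** These used 175 per arm (about 194 × 0.9 = 174.6), with SDs, effects and worst-rank shares assumed. With 15% (control) and 12% (device) at the worst rank, the adjusted/unadjusted variance ratios were:

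| rho | KCCQ-like | LVEF (entry at most 35%) | Walk (175-375 m) |
|---|---|---|---|
| 0.3 | 0.85 | 0.91 | 0.95 |
| 0.5 | 0.91 | 0.97 | 0.995 |
| 0.7 | 0.96 | 1.00 | 0.99 |

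KCCQ-like power rose from 44.7 to 50.7%, 57.5 to 61.1% and 74.9 to 76.1%: gains of 6.0, 3.6 and 1.2 points.

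Further runs under other assumed SDs and effects gave:
- KCCQ-like score: 4-16% lower variance and 2 to 8 power points.
- Range-restricted baseline such as the walk: 0-4% lower variance and -1 to +2 points, with one set giving 0.5 to 4 points at 15%/12%.
- At 29%/24% at the worst rank: 2 to 4 points for KCCQ and 1 to 2 for the walk.
- At 41%/35%: 0.2 to 1.4 points for the walk.

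Type I error of the adjusted test stayed near 5%.

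**The case against.** **The sentences quoted define the outcome, not the test.** A baseline-adjusted analysis of change is compatible with all of them, and the method is deferred to the SAP. This stands. A reader might infer that the formal tests are unadjusted; the available text shows only that the protocol specifies no adjustment.

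**The gain is smallest where the hierarchy is most exposed.** Positions 1 and 2 are both the walk, and LVEF is third. KCCQ, the one endpoint with a consistent gain, is last and blocks nothing. This also stands. A reader might infer that adjustment guards against an early near miss closing the sequence; the figures do not support that.

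**The worst-rank share may be higher than 12-15%.** The sample-size justification cites 84% freedom from death at 6 months in its reference cohort. Under a constant hazard, 1 - 0.84² = 29% would be dead by 12 months and 1 - 0.84³ = 41% by 18 months, before VAD or transplant is counted. That cohort is a proxy, and Exclusion Criterion 21 removes patients with expected survival under 2 years, so these shares are a caution, not a forecast. They push the gain towards the lower end.

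**Two supporting arguments add little.** Scoring subjects unable to walk as 0 makes their change equal to minus their baseline, but in a rank test most of them sit near the bottom anyway, and the calculations do not isolate this effect. The covariate list that omits LVEF is open-ended and exploratory, so adding LVEF to it would change no formal test.

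**Conclusion.** The point holds as one of efficiency and specification. The protocol specifies no baseline adjustment for the formal tests of four of the six hierarchical secondaries. A reader might infer bias or Type I error inflation, but an unadjusted comparison of randomized arms is valid.

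With rho 0.3 to 0.7 and 12-29% at the worst rank, the reduction in variance is:
- KCCQ-like score: roughly 4-16%, worth about 2 to 8 power points (1.2 in the least favourable single run).
- LVEF: 0-9%, simulated only at 12-15% worst rank.
- 6-minute walk: about 0-5%, little or nothing in power terms.

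The 10-35% reductions from the k = 1 formula (rho 0.8 to 0.3) should not be quoted as the expected benefit, because they assume equal SDs and no worst-rank subjects, which is not the planned analysis. Every figure rests on assumed SDs, effects, correlations and worst-rank shares; the documents give none for these endpoints. The case for acting is that the change is cheap, with no meaningful expected loss of precision, and not that the gain is large.

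**What to change.** First check the SAP. If it already pre-specifies baseline adjustment for these endpoints, nothing more is needed.

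If it does not, pre-specify before unblinding that endpoints 1, 2, 3 and 6 are compared by rank analysis of covariance: rank the improvement score with the planned worst-outcome ranks kept, use the endpoint's own baseline value as covariate (ranked, as in the simulations in step 3), and compare the arms on the residuals. For LVEF this means putting its baseline in the formal model; adding it to the exploratory list would not do the job.

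The cost is SAP wording and a few lines of code. No new data are required, and the endpoint definitions, worst-outcome rule and testing order are unchanged.
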